4.6.1 Primary outcome

The primary outcome measure is peak oxygen consumption on bicycle ergometry (i.e. peak VO_2), because this outcome is strongly associated with activity intolerance and may well correlate with subjective fatigability which we believe to be the most important determinant of quality of life in these patients. Peak VO_2 will be assessed at baseline and in the final week of each treatment phase.

4.6.2 Secondary outcomes

- 1. Monolysocardiolipin/tetralinoleoyl-cardiolipin MLCL/L4-CL ratio/cardiolipin profile in blood cells
- 2. PCr/ATP ratio in cardiac muscle on 31P Magnetic Resonance Spectroscopy
- 3. Skeletal muscle oxidative function/ on 31P Magnetic Resonance Spectroscopy
- 4. Quality of life (QoL) assessed using age-appropriate PedsQL questionnaires
- 5. Absolute neutrophil count
- 6. Amino acid expression (serum arginine and cysteine levels)
- 7. Cardiac function (LVEF and shortening fraction)
- 8. Mitochondrial size in lymphocytes
- 9. Numbers of mitochondria (per lymphocyte)
- 10. Total area of mitochondria per lymphocyte
- 11. Area of mitochondria as proportion of cytoplasm
- 12. Mitochondria function and cristae organisation in lymphocytes
- 13. Arrhythmia profile from 12 lead ECG at rest and during exercise (for potential rhythm abnormalities)

See Section 5.6 Data Collection for the timing of these assessments.

The work around the immortalised cell lines does not form part of this protocol and will be described in a separate protocol.

In addition to the data collected from the clinical trial we propose to integrate qualitative research methods in order to explore patients' and families' experiences of the different interventions. Parents of younger patients (<18 yrs) and patients (>14yrs, suitability for interviewing to be determined on advice from the Clinical Psychologist known to the patient) will be invited to take part in semi-structured one-to-one interviews in the assessment periods after the first and second interventions. The first interview will last approximately 20 minutes and explore the parents'/participant's experience of the intervention. The second interview will last

approximately 40 minutes and will explore the parents'/participant's experience of the second intervention and their perception of participating in the trial as a whole. Interviews with patients and parents will be digitally recorded with their consent and transcribed verbatim. Data from interviews will be analysed using framework analysis methodology [15] with the aid of the NVivo software package.

4.7 Sample size calculation

This is a single centre study to be performed in patients attending the NHS National Barth Syndrome Service at UH Bristol. A total of 18 males aged between six and 24 years currently attend the service. We anticipate that between 12 and 15 UK patients are likely to consent to take part.

In a simple crossover trial (a single intervention and control comparison), the standard deviation (SD) of the within subject difference between treatments is given as: sqrt (2 x within subject SD) [16]. In a crossover trial, all participants constitute their own control.

In this trial, the difference in mean peak volume of O_2 consumption between placebo and bezafibrate phases will be tested, assuming a 2-tailed alpha of 0.05. For a sample size of 12 participants, the trial will be able to detect a difference of 0.90 (within subject) SDs with 80% power, or 1.05 SDs with 90% power.

5. Trial methods

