5.12 Likely rate of loss to follow-up

As all of the potential participants are already well known to the research team and would use the Barth Syndrome Service outside of this study, we do not anticipate there to be any loss to follow-up. Therefore there are no special features to minimise attrition bias. Established CTEU methods will be used to maximise the proportion of participants for whom all outcome data are available and the proportion of participants who receive the intervention to which they were allocated.

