6.1 Plan of analysis

It is hoped that all participants will complete and contribute data to both phases of the crossover study, although we recognise that some missing data are likely due to the fragile nature of Barth syndrome.

We aim to retain all participants in the trial for the full duration of 10 months follow-up, irrespective of any periods when an intervention has to be suspended because of ill health. The only exceptions will be when a participant expressly requests to end all aspects of their participation in the trial or cannot continue because of deteriorating health. We propose that primary analyses should respect the intention-to-treat principle but envisage that additional secondary or sensitivity analyses may be specified in a detailed analysis plan, written prior to completing the final data queries for final analyses.

Our plan for analyses assumes that the continuously scaled outcome data (or transformed data) will be distributed satisfactorily to allow parametric methods to be applied. We propose to analyse the data using mixed effects regression methods that will allow for participants' data to be included if not complete. The regression models will estimate effects for both the treatment factor (2 levels) and time period of intervention (2 levels), adjusting for baseline assessments of outcomes at the time of recruitment.

Participants will be fitted as random effects. We will test for the presence of a carry-over effect (i.e. the possibility that results obtained during the second treatment phase are affected by what happened in the first treatment phase) by including a treatment-by-time period interaction in the model. We expect that this interaction effect will not be statistically significant.

Similar methods will be used for analyses of the additional objectives to ensure that (a) the data hierarchy is respected (i.e. repeated measurements within subjects) and (b) available data for all participants can be included. Regression models will be fitted to estimate differences in

secondary outcomes when treated with bezafibrate vs. placebo and, additionally, to quantify the extent to which more 'proximal' biomarkers are associated with more 'distal' clinical and symptomatic outcomes.

Non-adherence to random allocations will be documented and every effort will be made to include all randomised participants.

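### Protocol section 4.7 states its detectable difference in the wrong SD unit: 0.90 and 1.05 are multiples of the SD of the within-subject difference, not of the within-subject SD

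*Protocol*

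**What the plan says.** Protocol section 4.7 introduces two standard deviations and links them: "the standard deviation (SD) of the within subject difference between treatments is given as: sqrt (2 x within subject SD" (closing bracket follows). The first is the SD of each participant's bezafibrate-minus-placebo difference. The second is the within-subject SD, the spread of repeated measurements on one person.

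The next paragraph but one gives the power claim. The comparison is set out as "the difference in mean peak volume of O_2 consumption between placebo and bezafibrate phases will be tested", "assuming a 2-tailed alpha of 0.05". The claim then reads "For a sample size of 12 participants", the trial can "detect a difference of 0.90 (within subject) SDs with 80% power, or 1.05 SDs with 90% power".

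The section gives no difference in peak VO2 in absolute units and no SD value, so the SD multiple is the protocol's only statement of what the trial can detect.

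Section 6.1 says that the regression models will "estimate effects for both the treatment factor (2 levels) and time period of intervention (2 levels"), so period is fitted alongside treatment. The same section says "we recognise that some missing data are likely due to the fragile nature of Barth syndrome".

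**The concern.** The unit in the power claim carries the name of the smaller of the two SDs that the section has just distinguished. They differ by a factor of the square root of 2, about 1.41. A multiple that is right for one is therefore wrong for the other by that factor, and at this sample size the effect on power is large.

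The conversion formula cannot be used to repair the label, because it is wrong as well. The square root of twice an SD is not in the units of the outcome.

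What is at stake is how the result is read. Anyone who wants the detectable difference as a peak VO2 value has to supply an SD, and the text points to a within-subject (repeatability) SD. With that SD the reader would understate the detectable difference by 1 − 0.90/1.27 = 29%. A null result could then be taken as stronger evidence against a moderate effect than it is.

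**Working it through.** **Inputs.** n = 12 complete pairs, two-sided alpha 0.05, effects 0.90 and 1.05, stated power 80% and 90% (all section 4.7). Degrees of freedom are 12 − 2 = 10 with period fitted (section 6.1), or 12 − 1 = 11 for a plain paired t test.

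**Relation between the SDs.** If each of the two measurements has within-subject variance SDw², their difference has variance 2 × SDw². Hence SDdiff = sqrt(2 × SDw²) = sqrt(2) × SDw.

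**Power formula.** With d = difference / SDdiff, the test statistic follows a non-central t distribution with non-centrality d × sqrt(12). Power is the probability that it falls beyond the two-sided 5% critical value, which is 2.228 for 10 df and 2.201 for 11 df.

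**Step 1: reproduce the stated figures, with the effect in SDdiff.**

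| Effect | Non-centrality | Power, 10 df | Power, 11 df | Stated |
|---|---|---|---|---|
| 0.90 | 0.90 × 3.464 = 3.118 | 80.2% | 81.0% | 80% |
| 1.05 | 1.05 × 3.464 = 3.637 | 90.5% | 91.1% | 90% |

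Solved exactly, the detectable d is 0.898 (80%) and 1.040 (90%) with 10 df, or 0.889 and 1.029 with 11 df. The protocol's figures match in this unit.

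**Step 2: the same effects in SDw, the unit printed.** Divide by sqrt(2) to obtain d.

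| Effect | d | Non-centrality | Power, 10 df | Power, 11 df | Stated |
|---|---|---|---|---|---|
| 0.90 SDw | 0.636 | 2.205 | 51.3% | 52.0% | 80% |
| 1.05 SDw | 0.742 | 2.572 | 64.1% | 64.9% | 90% |

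No other choice of test rescues the label. At 0.90 SDw a two-sided normal approximation gives 59.7%, a one-sided t test 66.3% and a one-sided normal approximation 71.2%.

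**Step 3: what 12 pairs can detect in SDw (10 df).**
- 80% power: 0.898 × 1.414 = 1.27 SDw
- 90% power: 1.040 × 1.414 = 1.47 SDw

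**Step 4: size needed for the claim as labelled.** With 21 participants, power is 79.2% at 0.90 SDw and 89.9% at 1.05 SDw (paired t); 22 are needed for both. Section 4.7 counts 18 patients in the age range. All 18 would give 72% at 0.90 SDw.

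**Step 5: the printed formula taken literally.** If SDdiff were sqrt(2 × SDw), then 0.90 SDw would give d = 0.90 × SDw / sqrt(2 × SDw), which changes with the measurement unit. Numerically, SDw = 0.5 gives 30% power, SDw = 1 gives 52%, and SDw = 4 gives 98% (11 df). Power cannot depend on the scale on which VO2 is recorded, so the expression is a misprint of sqrt(2) × SDw.

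**Step 6: fewer complete pairs.** With 10 pairs and 8 df, the detectable d is 1.012 (80%) and 1.174 (90%), which is 1.43 and 1.66 SDw.

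**The case against.** The strongest reply is that nothing was miscalculated. The figures are right for the SD of the within-subject difference, which is the quantity that the test uses, and the bracketed words in the power claim may be loose shorthand for it. That is plausible as intent and limits the point to a label and a formula. It does not remove the point, because the same section has already given those words to the other SD.

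It can also be said that nothing in the trial turns on the label. Enrolment is capped by the number of patients who exist, and 4.7 reports what 12 participants can detect instead of deriving 12 from a target effect. The interim rule and the planned mixed model do not use the multiple. The section on dissemination already concedes that a larger international trial would have been preferable on grounds of power. All of this stands, and it keeps the point at the level of a correction to the text.

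Two stronger readings are tempting. A reader might infer that the trial is designed with about half the power that it claims. The documents do not support this: 51% applies only if 0.90 is taken in the printed unit, and the design delivers 80% at 0.90 in the unit in which the figure was evidently computed.

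A reader might also set section 5.12 ("we do not anticipate there to be any loss to follow-up") against section 6.1, which expects missing data, and call it a contradiction. It is not. The first concerns losing contact with patients whom the service already knows. The second concerns data missing through illness, and a participant who stays in contact can still miss an assessment. Section 6.1 also plans a mixed model that keeps incomplete participants.

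**Conclusion.** The point holds as an error of unit and notation in the protocol's only power statement. Read as written, power is overstated by about 29 percentage points at 0.90 (51% against 80%) and about 26 at 1.05 (64% against 90%). Equivalently, the detectable difference in within-subject SDs is 1.27 and 1.47, not 0.90 and 1.05.

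These figures assume 12 complete pairs, a two-sided 5% test, period fitted (10 df) and equal within-subject variance in the two periods. Using 11 df instead moves power by less than one percentage point. The within-subject SD of peak VO2 is not given, so none of this can be turned into an absolute VO2 difference from the protocol alone.

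**What to change.** In section 4.7:

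1. Correct the conversion to: SD of the within-subject difference = sqrt(2) × within-subject SD.
2. Restate the claim along these lines: with 12 complete pairs and a two-sided 5% test, the trial can detect 0.90 (80% power) or about 1.04 to 1.05 (90% power) SDs of the within-subject difference, that is, about 1.27 or 1.47 within-subject SDs.
3. Optionally, note that the figures need 12 complete pairs, since 6.1 expects some missing data, and give the values for 10 pairs: 1.43 and 1.66 within-subject SDs.

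Section 5.12 needs no change on this account, and neither do enrolment, design or analysis. The cost is a few words and a less favourable statement of sensitivity in within-subject SDs.

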5.1 Description of randomisation

The random sequence allocations of bezafibrate or placebo will be generated prior to the start of the study by a CTEU statistician, using blocks of undisclosed size. The sequence will then be 'attached' to a list of consecutive study IDs and provided to the clinical trials pharmacy department.

The allocations of drug or placebo in the second phase of the trial will be the opposite of the first phase. Once a participant has given consent and eligibility has been documented and confirmed, they will be allocated to the next consecutive study ID. A doctor will prescribe the study 'medication' and the pharmacy will dispense the appropriate intervention according to the participant's study ID and phase in the trial.

Allocation concealment will minimise selection bias. The sequence of random allocations will be generated by computer and will be concealed from all clinical and research personnel.

5.2 Blinding and code breaking

This study is double blinded: neither the participants nor investigators (or any other member of the research team apart from the pharmacist) will have knowledge of the allocated treatment being given, or the order in which it is given.

The tablets containing bezafibrate or placebo do not have a particularly strong or unusual smell or taste, so we do not anticipate un-blinding will occur due to the characteristics of the drug. The tablets for active drug and placebo will look identical, which should help to minimise the unblinding of participants and subsequently investigators. We are aware that bezafibrate may induce side-effects in some patients that will inadvertently un-blind participants and we acknowledge this may be a limitation of this study.

The patient information leaflet and the process of informed consent will explain the uncertainty around the potential beneficial effects of bezafibrate over a placebo. Therefore, in the event of inadvertent un-blinding of a participant, the participant should not have a strong expectation that one or other method should lead to a more favourable result.

Participants will be made aware before entering the study that they will not be told which treatment they will receive in each phase. Doctors will prescribe the 'study medication' rather than specifically bezafibrate or placebo and the prescription for the 'study medication' will be sent to pharmacy, who will then provide the medication as specified according to the predetermined list drawn up by the study statistician prior to recruitment (as described earlier). The allocations will only be known by pharmacy and the study statistician and will not be disclosed to any other member of the research team.

Members of the health care team can request un-blinding of the study medication in either phase in the event of a serious adverse event (SAE), if they consider that this information will alter their management of the SAE. During office hours CTEU Bristol should be contacted for requests to unblind. Out of office hours UH Bristol Pharmacy Department should be contacted using their on-call system and a request made to contact a member of the Clinical Trials Pharmacy team. The on call pharmacist will have access to the un-blinding list. All instances of un-blinding will be documented, including who requested the un-blinding, why it was required, the time and date and who performed the un-blinding.

5.3 Research procedures

Detailed assessments will be performed in Bristol at baseline and at the end of each treatment phase. These assessments will be timed during the final week of therapy so that patients are still receiving interventions/placebo at the time of testing but will have had maximum cumulative exposure to the drug or placebo. These will include:

- Anthropometric data (height and weight)
- Medical history and examination (including resting blood pressure, heart rate and oxygen saturation)
- Trans-thoracic echocardiographic determination of cardiac function at rest and during exercise (stress Echo) (see Appendix 1).
- Tissue Doppler studies (see Appendix 1).
- Modified McMaster exercise protocol to assess peak oxygen consumption using an electronically braked GE Healthcare exercise echocardiography
- Muscle deoxygenation (HHb) during exercise using near infrared spectroscopy (NIRS) over the vastus lateralis muscle.
- Ventricle volumetrics using cardiac Magnetic Resonance Imaging (MRI)
- PCr/ATP ratio obtained from Magnetic Resonance Spectroscopy
- Quality of Life questionnaires (PedsQI)
- Qualitative assessments (semi-structured one-to-one interviews) to assess patient experiences of the intervention and participating in a trial as a whole, along with a dietary evaluation
- Cardiac arrhythmia profile from 12 lead ECG at rest and during exercise

In those who can tolerate an MRI scan lasting approximately one hour without general anaesthetic, we will use 31P magnetic resonance spectroscopy (performed on a Siemens 3T Magnetom Skyra MRI scanner) to assess phosphocreatine/adenosine triphosphate ratio (PCr/ATP) in myocardium and oxidative function (PCr recovery kinetics) in skeletal muscle. Cardiac MRI imaging will assess ventricle volumetrics. Detailed MRI/S methods will be documented in a separate protocol.

Imaging tests will be performed at the Clinical Research Imaging Centre (CRIC, a joint UoB/UHBristol facility).

A total of 20 mL of blood will be taken at each assessment visit for the following tests:

- 1. At baseline only: establishment of an EBV transformed lymphoblast line* for *in vitro* incubation with resveratrol or bezafibrate and assessment of cardiolipin ratio.
- 2. At baseline and end-of-treatment assessments: Full blood count, absolute neutrophil count, urea/electrolytes, liver function tests, creatinine kinase, plasma arginine/cysteine, full lipid profile (total cholesterol, high density lipoprotein, triglycerides), brain natriuretic peptide (as a blood marker of LV function).
- 3. Mitochondrial tests: assessment of detailed cardiolipin profiling (to be performed at Great Ormond Street Hospital) and calculation of MLCL/L4-CL ratio. Mitochondria of the blood cells will be examined by electron microscopy of lymphocytes and measurements of size, number and shape recorded. This work will be performed at the University of Bristol. Lymphocytes extracted from 5 mL whole blood will undergo analysis for mitochondrial function studies including analysis of respiratory chain enzyme complexes using established spectrophotometric methods.

* For patients who have an existing EBV cell line available from a separate study entitled 'Cardiolipin metabolism and mitochondrial dysfunction in the pathogenesis of Barth syndrome', consent will be sought to use their existing cell line, rather than establish a new one.

Informed consent will be sought from the patients and/or their families to store and use the EBV transformed lymphoblast lines (also known as 'immortalised' cells) for future research.

Subjective quality-of-life will be assessed using age appropriate Peds QLTM Paediatric Quality of Life Inventory assessment forms and parental questionnaires. These include forms suitable for young adults (18-25).

5.4 Duration of treatment period

The duration of the treatment period will be for a minimum of 9 months in total: 4 months of bezafibrate followed by 4 months of placebo (or vice versa), with a minimum washout period of one month in between, where no treatment is given between the two treatments.

If the DMSC deem it necessary for an interim analysis after the first phase of treatment and no effect of bezafibrate is found, the study may not continue on to the second phase. If this happens, the duration of treatment will be four months.

5.5 Definition of end of trial

The end of the trial for participants will be after they have completed the treatment period and a one month follow-up period (or have been lost to follow-up or died).

The end of the trial as a whole will be when all recruited participants have completed the treatment and follow-up period **and** all data has been collected, data queries answered and all laboratory samples have been processed and analysed.

5.6 Data collection

Data collection will occur at four different time-points: baseline, end of treatment phase 1, end of treatment phase 2 and after completion of one month follow-up.

A schedule of investigations and assessments over the 10 months of the trial is shown below.

Table 1Schedule of Events

Event Month		Baseline	Phas	e 1	Washout Period				e 2	Follow-up		
		0	1	2	3	4	5	6	7	8	9	10
Informed Consent		v										
Height & weig	ght	×				~					~	
Medical histor	ry	v										
Clinical exam	ination+	\checkmark				~					~	
Bicycle ergometry	Peak oxygen consumption	~				*					~	
(exercise bike test)	Muscle deoxygenation (HHb) (NIRS)	~				~					~	
	Tissue Doppler studies	~				~					~	
Echocardiogram (at rest and during exercise)*		~				~					~	
12 Lead ECG at rest and during exercise (during echo)		r				~					~	
Blood sample (20-30 ml total) [#]	e Transformed lymphoblast line for in vitro incubation with Bezafibrate and Resveratrol	V										
	FBC, absolute neutrophil count, urea/electrolytes, LFTs, CK, plasma arginine/ cysteine, full lipid profile (total cholesterol, high density lipoprotein, triglycerides), brain natriuretic peptide	×				r					~	
	Mitochondrial assessment [#]	V				~					~	
Blood sample (safety assessment) done locally to patient	 FBC including absolute neutrophil count, routine renal and liver function tests, plasma triglyceride/total cholesterol/LDL- 		v	~	~		×	v	~	v		

CARDIOMAN Protocol – version 3.0 04 October 2018

Event		Baseline	Phase 1				Washout Period	Phase 2			Follow-up	
	cholesterol and Creatine Kinase, Creatinine**											
Month		0	1	2	3	4	5	6	7	8	9	10
Cardiac/skeletal muscle MRI/MRS scan ^{\$}		V				~					~	
QoL: /Paeds Q	QoL: /Paeds QoL					✓					~	
Adverse events	Adverse events		~	~	v	✓	×	~	~	√	~	\checkmark
Drug prescribir	Drug prescribing											
Drug dispensing		×		√	√	✓		v	√	~	~	
Qualitative Interview						~					~	
						(20 mins)					(40 mins)	

+ Including resting blood pressure, heart rate and oxygen saturation

* Cardiac status: LVEF and shortening fraction

Samples for detailed cardiolipin profiling and calculation of MLCL/L4-CL ratio; examination of mitochondria of the blood cells by electron microscopy and measurements of size, number and shape recorded; analysis of mitochondrial function studies including analysis of respiratory chain enzyme complexes.

**to be measured at 2 weeks after initiated study drug in both phases for participants who have had an organ transplant

\$ Cardiac MRI will be used to assess:

• Right and left ventricle volumetrics.

MRS will be used to assess:

- Phosphocreatine/adenosine triphosphate ratio (PCr/ATP) in myocardium and oxidative function
- ATP production in skeletal muscle.

Monthly blood tests will be performed throughout the study at the patient's local hospital or GP surgery to assess the continuing safety of the bezafibrate in this population. An additional blood test for creatinine will be carried out at 2 weeks after the initiation of study drug in both phases in participants who had had an organ transplant. Absolute neutrophil count, routine renal and liver function tests, plasma triglycerides/total cholesterol/LDL-cholesterol and creatine phosphokinase will be tested. The study research nurses will facilitate the arrangement of these tests with the patients/families and their local provider and will obtain the results from the place of testing for safety monitoring.

